7.5.2.2 CYP1A2 Activity test

Cytochrome P450 1A2 activity will be measured at Day 0 and at Day 5. Measurement of enzyme activity will be assessed through PX and CAF plasma molar concentrations approximately 6 hours (± 15 minutes) after the intake of a cup of coffee made from 4.2 g ($\pm 10\%$) regular instant coffee (Nescafé Gold Instant; Nestlé; Deutschland; CAF content: 72 mg/2 g) with 150 ml ± 10 ml water. The CAF content will be approximately 150 mg CAF (Faber and Fuhr, 2004). The exact time of the intake of the cup of coffee in the morning and of the blood sampling (taken 6 hours [± 15 minutes] after the intake of the coffee) must be recorded. Cytochrome P450 1A2 activity will be assessed by the measurement of the molar PX/CAF metabolic ratio (Faber and Fuhr, 2004).

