**Table 18. Expected power (YVD-CS01-EU and ZRHX-EX-01 studies assumptions)**

| Assumptions | Reduction | | | | | |
|-------------|-----------|------|-----|-----|-----|-----|
| | 50% | 51% | 52% | 53% | 54% | 55% |
| YVD-CS01-EU | 96% | 91% | 85% | 75% | 63% | 48% |
| ZRHX-EX-01 | >99% | >99% | 96% | 81% | 48% | 16% |

A total of 160 smokers (80 in THS 2.2, 40 in CC, and 40 in the SA arm) will be randomized to demonstrate to demonstrate a reduction of at least 50% on 4 primary BoExps in smokers switching from CC to THS 2.2 as compared to those continuing to smoke CC, using one-sided test with 2.5% type I error probability.

Power considerations related to secondary endpoints of biological changes:

The sample size is sufficient to obtain 95% CIs for the ratio between (geometrical) mean levels of primary BoExps in THS 2.2 and SA see Section 12.2 with upper and lower limits deviating not more than 18% from the point estimates, with an 80% overall probability of achieving the desired precision of estimating the true mean.

This study has 80% power using a one-sided test with 2.5% type I error probability:

- To detect a 0.631 [ml/min/kg] (29%) difference between THS 2.2 and CC in CYP1A2 activity, as measured by the CAF clearance, assuming a standard deviation of 0.564. Effect size and variability are derived from data obtained in the YVD-CS01-EU study sponsored by PMI.
- To detect a 24.71 [ng/g creatinine] (20%) difference between THS 2.2 and CC in 11-DTX-B2, assuming a standard deviation of 43.78, as reported by Saareks et al, 2001. The anticipated effect size of THS 2.2 is assumed to be about 90% of the effect of smoking cessation reported in the paper by Saareks et al, 2001.

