7.1.4 CYP1A2

CYP1A2 activity is calculated as the molar metabolic ratio of PX / CAF in plasma, both expressed in molar equivalent (nmol/L).

The conversion factor will be applied as follows:

PX	The molecular weight is 180.166 g/mol (Chemical Information Specialized Information Services RN:611-59-6). Therefore to convert PX in ng/mL to nmol/L the result in ng/mL is multiplied by 5.550.
CAF	The molecular weight is 194.193 g/mol. (Chemical Information Specialized Information Services RN:58-08-2). Therefore to convert CAF in ng/mL to nmol/L the result in ng/mL is multiplied by 5.150.

The converted results will be calculated to three decimal places and the ratio will be reported as a percentage with two decimal places.

If either of the PX or CAF concentration is LLOQ then the ratio will not be calculated.

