**Table 13: Expected Power (YVD-CS01-EU and ZRHX-EX-01 Studies Assumptions)**

Assumptions	Reduction					
	50%	51%	52%	53%	54%	55%
YVD-CS01-EU	96%	91%	85%	75%	63%	48%
ZRHX-EX-01	>99%	>99%	96%	81%	48%	16%

A total of 160 smokers (80 in THS 2.2, 40 in CC, and 40 in the SA arm) will be randomized to demonstrate a reduction of at least 50% on 4 primary BoExp in smokers switching from CC to THS 2.2 as compared to those continuing to smoke CC, using one-sided test with 2.5% type I error probability.

The sample size is sufficient to obtain 95% CIs for the ratio between (geometrical) mean levels of primary BoExp in THS 2.2 and SA with upper and lower limits deviating not more than 18% from the point estimates, with an 80% overall probability of achieving the desired precision of estimating the true mean.

This study has 80% power using a one-sided test with 2.5% type I error probability:

1. To detect a 0.631 [mL/min/kg] (29%) difference between THS 2.2 and CC in CYP1A2 activity, as measured by the CAF clearance, assuming a standard deviation (SD) of 0.564. Effect size and variability are derived from data obtained in the YVD-CS01-EU study sponsored by PMI.
2. To detect a 24.71 [ng/g creatinine] (20%) difference between THS 2.2 and CC in 11-DTX-B2, assuming a SD of 43.78. The anticipated effect size of THS 2.2 is assumed to be about 90% of the effect of smoking cessation.

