12.1.5 Handling of Dropouts or Missing Data (including outside the limits of quantification)

In general, missing data will not be imputed in this study, due to the nature of the measurements and the short periods of exposure and use. However, for questionnaire data total scores and domain or subscale scores may use a certain degree of imputation (by averaging across individual item scores) as detailed in Section 7.3 "Questionnaires".

Laboratory parameters will be presented as detailed in Section 7.1 "Biomarkers".

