12.6.2.4 CYP1A2 Activity

CYP1A2 activity will be measured in plasma on Day 0 and Day 5. In this study the CYP1A2 activity will be calculated using the molar ratio of PX and CAF, as described in Section 7.1.4 “CYP1A2”. Descriptive statistics of the values and percent change on Day 5 from Day 0 and supportive listings will be provided.

The analysis will compare the Day 5 values between the THS 2.2 and CC arms and between the THS 2.2 and SA arms. An ANOVA model will be used with terms for sex, average daily CC consumption over the last 4 weeks as reported during screening and product. No adjustment will be made for multiple comparisons.

The SAS code will be the same as described in Section 12.6.1.1 “Primary Biomarkers of Exposure in 24 hour collection”, with no baseline value being included in the model.

LS means for each product along with the difference (THS 2.2 - CC) and 95% CI will be presented in the tables.

CYP1A2 activity will also be examined to compare the observed reductions in THS 2.2 vs. SA using the same methodology as above.

The data will be presented in the below outputs, the TFL number refers to the TFL number in the accompanying TFL shell document:

TFL number	Title
TABLES	
15.2.4.50	Descriptive Statistics of CYP1A2 Activity (%) – FAS
15.2.4.51	Analysis of CYP1A2 Activity (%) on Day 5 to 6 – FAS
LISTINGS	
15.3.4.1	Listing of CYP1A2 Activity and Changes from Baseline

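### CYP1A2: the stated 80% power does not follow from its own inputs and refers to caffeine clearance, not the PX/CAF ratio analysed; the Day 5 model also omits the measured Day 0 ratio

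*Protocol*

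**What the plan says.** Protocol 12.2, in its remarks on secondary endpoints, states 80% power at one-sided 2.5% "To detect a 0.631 [ml/min/kg] (29%) difference between THS 2.2 and CC in CYP1A2 activity, as measured by the CAF clearance", assuming an SD of 0.564. Effect and SD are attributed to an earlier sponsor study. SAP 8 repeats the claim: "To detect a 0.631 [mL/min/kg] (29%) difference between THS 2.2 and CC in CYP1A2 activity, as measured by the CAF clearance". The arms are 80 THS 2.2, 40 CC and 40 SA.

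The endpoint is defined on another scale. Protocol 7.5.2.2: "Cytochrome P450 1A2 activity will be assessed by the measurement of the molar PX/CAF metabolic ratio". SAP 7.1.4 adds that "the ratio will be reported as a percentage with two decimal places". Neither document derives a clearance.

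On timing, SAP 12.6.2.4 says "CYP1A2 activity will be measured in plasma on Day 0 and Day 5". It then specifies an ANOVA on the Day 5 values with sex, cigarette consumption and product, using the code of SAP 12.6.1.1 "with no baseline value being included in the model". Day 0 enters only the descriptive percent change and the listing.

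**The concern.** A power statement should be reproducible from the effect, SD, arm sizes and alpha printed beside it. This one is not, so at least one printed number is wrong. If that number is the SD, a value about half the true one stands in both documents and could be reused in a later design. The statement also tells the reader nothing about the analysis that will be run, because no effect size or SD is given for PX/CAF.

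The model is a separate matter. The ratio is measured in every arm before exposure, and the objective is to describe changes in CYP1A2 activity, yet the comparison ignores the Day 0 value. What is at stake is precision: intervals for THS 2.2 versus CC and THS 2.2 versus SA that are wider than the collected data require.

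**Working it through.** **Power as stated.** Inputs from Protocol 12.2 and SAP 8: difference 0.631, SD 0.564, 80 versus 40 subjects, one-sided 2.5%, stated power 80%.

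- SE = 0.564 × √(1/80 + 1/40) = 0.1092
- Noncentrality = 0.631 / 0.1092 = 5.78
- Power (noncentral t, 118 df) = 0.9999; the normal approximation also gives 0.9999

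The stated 80% is not reproduced. Alternative readings do not recover it either:

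| Reading | Power |
|---|---|
| 40 versus 40 | 99.9% |
| 50% dropout | 98.0% |
| SD × √2 | 98.3% |
| 0.564 as a variance | 99.1% |
| 0.564 as a log-scale SD, change of ln 0.71 / ln 1.29 | 88.0% / 64.5% |
| 0.564 as a CV, same two changes | 92.0% / 70.6% |

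**What 80% would require** (noncentral t, one input changed at a time):

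- Difference: 0.3085 mL/min/kg. The reference mean implied by the text is 0.631 / 0.29 = 2.176, so this is 0.3085 / 2.176 = 14.2%.
- SD: 1.154, which is 1.154 / 0.564 = 2.05 times the printed value.

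**Check of the method on the companion statement.** For 11-DTX-B2 the same paragraph gives a difference of 24.71 and an SD of 43.78. SE = 43.78 × √(1/80 + 1/40) = 8.48; noncentrality = 24.71 / 8.48 = 2.91; power = 82.4%. That is close to the stated 80%, so the CYP1A2 line is the outlier.

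**Scale.** Clearance is in mL/min/kg; the analysed variable is a unitless molar ratio. With no conversion and no PX/CAF effect or SD, power for the analysed endpoint cannot be computed from the documents.

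**Baseline term.** The arm-comparison models for the biomarkers of exposure (SAP 12.6.1.1, 12.6.2.1), plasma nicotine and cotinine (12.6.2.2), the questionnaires (12.6.3.1), topography (12.6.3.2), CYP2A6 (12.6.3.4) and risk markers (12.6.3.6) all include baseline. The only other comparison without it is that of the nicotine and cotinine PK parameters (12.6.2.3), which come from a serial profile with no Day 0 counterpart.

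Let ρ be the Day 0 to Day 5 correlation given sex and consumption. It is not in the documents, so a range is assumed. The SE is multiplied by √(1 − ρ²):

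| ρ | SE factor | Reduction |
|---|---|---|
| 0.3 | 0.954 | 5% |
| 0.5 | 0.866 | 13% |
| 0.7 | 0.714 | 29% |
| 0.8 | 0.600 | 40% |

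At ρ = 0 there is a small cost. With all 160 subjects in the model the residual df before adding baseline are 160 − 5 = 155, and the expected SE factor is √(1 + 1/(155 − 2)) = 1.003, an increase of about 0.3%.

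**Subjects without a Day 0 ratio.** SAP 7.1.4: "If either of the PX or CAF concentration is LLOQ then the ratio will not be calculated"; SAP 12.1.5: "In general, missing data will not be imputed in this study". If a share q drops out of the adjusted model, the variance factor is (1 − ρ²)/(1 − q), so break-even is q = ρ². For the 120 subjects in THS 2.2 and CC that is 9% (about 11 subjects) at ρ = 0.3 and 25% (30 subjects) at ρ = 0.5.

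**The case against.** The strongest reply is that the 80% may be right and the SD mislabelled. The standardised 11-DTX-B2 effect is 24.71 / 43.78 = 0.564, the very figure printed as the CYP1A2 SD. If 0.564 was meant as a standardised effect, the SD is 0.631 / 0.564 = 1.12 and power is 82.3%, in line with the companion line. This is inference, and only the source study can settle it. It does not rescue the text, since an input is then wrong. It does mean that 99.99% should not be taken as the study's real power, and that the statement should not be rewritten before the source is checked.

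Other points on that side:

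- The statement openly says that it refers to clearance, and no rule requires a power figure for every secondary endpoint. True, but neither document says that clearance is not what will be analysed.
- Leaving out baseline is a permissible choice. The protocol requires baseline adjustment only for biomarkers of exposure, and the gain rests on an assumed correlation, taken as common to all arms. This stands: the point is about efficiency and is not an error.
- Day 0 plasma nicotine and cotinine exist and are also left out of the PK models. They are single evening samples, not the same parameters, so CYP1A2 remains the only comparison that leaves out a Day 0 value of the variable being analysed.

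**Conclusion.** The point holds in all three parts. The printed inputs give 99.99% power where 80% is claimed. The figure is for a quantity the trial does not derive. The Day 5 model leaves out a baseline that is measured.

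The consequences are modest. The trial is sized on the four primary biomarkers, so the number of subjects and the success criterion are unaffected. If only one of the three printed numbers (effect, SD, power) is wrong, true power on the clearance scale is about 80% or higher, so nothing suggests a shortfall on that scale. Randomisation keeps the planned ANOVA unbiased. The baseline gain depends on an unknown correlation: 5% to 40% in the SE for ρ from 0.3 to 0.8, against a cost of about 0.3% at ρ = 0. The change should be made, but the primary conclusion does not depend on it.

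**What to change.** **Power statement (Protocol 12.2 and SAP 8).** Check 0.631 and 0.564 against the earlier sponsor study. If both are confirmed, restate as more than 99.9% power for 0.631 mL/min/kg, or as 80% power for 0.31 mL/min/kg (14%). If the SD or effect is wrong, correct it. In either case, say that the figure refers to caffeine clearance and not to the analysed PX/CAF ratio, or replace it with a sourced PX/CAF figure, or delete it.

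**Model (SAP 12.6.2.4).** Remove the clause that excludes baseline and write, for example: *Day 5 PX/CAF ratios will be compared (THS 2.2 with CC, THS 2.2 with SA) by ANCOVA on the Day 0 ratio, sex, average daily CC consumption and product, with Day 0 and Day 5 ratios on the same scale. Subjects lacking a calculable Day 0 ratio will be counted and left out of this model. The model without baseline will be run as a sensitivity analysis on all subjects with a Day 5 ratio.* The section should also state whether that scale is logarithmic, since the code it borrows logs the data while the table is to show a difference.

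**Cost.** A source check, a few sentences and one covariate, settled before database lock, with no new data. A formal change to the protocol text is an amendment and goes to the ethics committee under Protocol 1.1. If that is not wanted for this alone, the correction can be made in SAP 8 and recorded in SAP 9. The adjusted model spends one degree of freedom and loses any subject without a Day 0 ratio, whom the sensitivity analysis retains.

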12.3 Analysis Population

The main population for non-safety analysis will be the full analysis set (FAS) population. The per-protocol (PP) population will be used only for the analysis of the primary endpoint to examine the robustness of the primary analyses.

Safety will be analyzed using the safety population.

12.3.1 Full Analysis Set

The FAS consists of all the randomized subjects who had at least one post-randomization product use experience, if randomized to THS 2.2 or CC, and have at least one valid non-safety assessment (THS 2.2, CC, SA arms).

Confidentiality statement: Data and information contained in this document are considered to constitute trade secrets and confidential commercial information, and the legal protections provided to such trade secrets and confidential information are hereby claimed under the applicable provisions of applicable law. No part of this document may be publicly disclosed without the written consent of Philip Morris Products S.A.

12.3.2 Per Protocol Population

The PP population is a subset of FAS and includes all randomized subjects who fulfill key compliance criteria of the protocol, and have no major protocol deviation (to be further described in the SAP).

12.3.3 Safety Population

The safety population consists of all the subjects who had at least one exposure to THS 2.2 (product test at Admission Day). Subjects in the safety population will be analyzed according to actual exposure.

12.4 Primary Analysis

12.4.1 Primary Endpoint Analysis Variables

The primary endpoints are:

- COHb on Day 5
- MHBMA on Day 5
- 3-HPMA on Day 5
- S-PMA on Day 5.

See section 3.4.1.

Evaluation Criterion: The study will be considered successful if the study demonstrates a 50% reduction or more for all four primary BoExp in the THS 2.2 arm compared to the CC arm (as measured on Day 5), using a one-sided test with 2.5% type I error probability.

12.4.2 Baseline Comparability

Not applicable.

12.4.3 Descriptive Analysis

Primary endpoints will be summarized as described in Section 12.1.3 on the FAS.

Should more than 20% of the subjects be excluded from the FAS population, the above descriptive analysis will be repeated on the PP population.

12.4.4 Confirmatory Analysis

The hypothesis to be tested for each of the primary and secondary biomarkers of exposure is that the geometric mean level on Day 5 of the biomarker for THS 2.2 is lower relative to CC.

Confidentiality statement: Data and information contained in this document are considered to constitute trade secrets and confidential commercial information, and the legal protections provided to such trade secrets and confidential information are hereby claimed under the applicable provisions of applicable law. No part of this document may be publicly disclosed without the written consent of Philip Morris Products S.A.

Analysis of BoExp will be conducted on the natural log scale. In order to test the follow hypothesis

Null hypothesis (H0): $m1 \geq m2$

Alternative hypothesis (H1): $m1 < m2$

Where $m1$ and $m2$ are the geometric means of the biomarker levels on Day 5 for THS 2.2 and CC respectively.

The transformed data will be analyzed by means of a generalized linear model using product arm as covariate adjusting for the following baseline information: sex, average cigarette consumption over the previous 4 weeks, and baseline value of endpoint. Estimates of differences between groups will be back-transformed to provide relative effects.

Assumptions of the analysis of variance model will be tested. Markedly non-lognormally distributed BoExp data will be transformed or analyzed by appropriate non-parametric methods.

Should more than 20% of the subjects be excluded from the FAS, would the above confirmatory analysis will be repeated on the PP population.

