**Study Population and Main Criteria for Inclusion:**

One hundred and sixty female or male smoking, healthy Caucasian adult subjects meeting the following main inclusion criteria:

- Subject is aged from 21 to 65 years (inclusive).
- Subject is Caucasian.
- Smoking, healthy subject as judged by the Investigator or designee.
- Subject smokes at least 10 commercially available non-menthol CCs per day (no brand restrictions) for the last 4 weeks, based on self-reporting.
- Subject has smoked for at least the last 3 consecutive years.
- Subject does not plan to quit smoking in the next 3 months.
- The subject is ready to accept 5 days of smoking abstinence.
- The subject is ready to accept using the THS 2.2 product.

Subjects who do not complete the study after randomization will not be replaced.

Investigational Product; Dose; and Mode of Use:

Test Product: Tobacco Heating System 2.2 (THS 2.2)

Reference product: The reference product to the THS 2.2 during the randomized exposure period is the subject's own preferred commercially available single brand of non-menthol CC

Reference Point: SA

Duration of Study:

The entire study duration per subject will be 17 to 44 days, including a Screening period of up to 4 weeks prior to baseline (Day -30 to Day -3), a 9-day confinement period (from Day -2 to time of Discharge on Day 6), followed by a 7-day safety follow-up period (until Day 13).

Statistical Methods:Statistical Analysis:

Analysis of BoExp will be conducted on the natural log scale. The transformed data will be analyzed by means of a generalized linear model using product arm as covariate adjusting for the following baseline information: sex, average cigarette consumption over the previous 4 weeks, and baseline value of endpoint. Estimates of differences between groups will be back-transformed to provide relative effects. Assumptions of the analysis of variance model will be tested. Markedly non-lognormally distributed BoExp data will be transformed or analyzed by appropriate non-parametric methods.

Unless stated otherwise, all statistical tests will be two-sided and conducted at the 5%

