5.5.2 Evaluation Criteria

The study will be considered successful if the study demonstrates a 50% or more reduction in MHBMA, 3-HPMA, S-PMA, and COHb in the THS 2.2 arm compared to the CC arm (as measured on Day 5), using a one-sided test with 2.5% type I error probability.

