12.6 Planned Statistical Analyses

Markedly non-lognormally distributed BoExp data will be transformed or analyzed by appropriate non-parametric methods with bootstrapping using the SAS procedure PROC SURVEYSELECT. The seed to be used in any analysis will be contained in the SAS output and will be different for each analysis.

For all statistical analysis data from all arms, THS 2.2, CC and SA will be included in all models.

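### An undefined switch away from the log-scale analysis is open for every primary BoExp, and nothing requires the replacement to estimate the geometric mean ratio that the 50% criterion uses

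*Protocol*

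**What the plan says.** Success is defined on a relative scale. SAP 5.5.2 asks for a "50% or more reduction in MHBMA, 3-HPMA, S-PMA, and COHb in the THS 2.2 arm compared to the CC arm". Protocol 12.4.1 likewise requires that the study "demonstrates a 50% reduction or more for all four primary BoExp", "using a one-sided test with 2.5% type I error probability".

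The planned analysis matches that scale. Protocol 12.4.4 models log values, and both it and the synopsis add that "Estimates of differences between groups will be back-transformed to provide relative effects". SAP 12.6.1.1 gives the ANCOVA code for the primary endpoints and reports the THS 2.2:CC ratio of geometric least squares means with its 95% CI.

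The same protocol section then says that the model assumptions will be tested, and that "Markedly non-lognormally distributed BoExp data will be transformed or analyzed by appropriate non-parametric methods". SAP 12.6, the preamble to all planned analyses, repeats this for BoExp data and adds bootstrapping through PROC SURVEYSELECT. On the random seed it says: "The seed to be used in any analysis will be contained in the SAS output and will be different for each analysis". SAP 12.6.1.1 and 12.6.1.2 do not exempt the primary endpoints from the preamble.

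Two further facts bear on this. Both documents write the null hypothesis as no difference between the geometric means, without the 50% margin (Protocol 12.4.4, SAP 12.6.1.2). SAP 12.6 also puts all three arms in every model, so the ANCOVA code uses one residual variance for THS 2.2, CC and SA.

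**The concern.** The fallback is an instruction to replace the confirmatory analysis, endpoint by endpoint, and it leaves open every element that would make it a rule. These are what counts as a marked departure, which test and threshold decide, which transformation or non-parametric method follows, what quantity that method estimates, and how the result is set against a 50% reduction.

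Two things are at stake. First, all four BoExp must succeed. If one is switched to a method that does not estimate the ratio, the criterion may not be decidable on its own terms for that endpoint, and so for the study. Second, a choice of method made with the results in view no longer guarantees the one-sided 2.5% level. COHb is the limiting endpoint. Where the other three have power near 1, any excess error on COHb passes almost unchanged to the study claim.

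**Working it through.** **1. The plan's own figure.** Inputs: 80 THS 2.2 and 40 CC subjects (Protocol 12.2); COHb ratio 0.40 with CV 0.32 (Protocol Table 16); margin 0.50; one-sided 2.5%.

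- Log SD = √ln(1 + 0.32²) = 0.312.
- SE = 0.312 × √(1/80 + 1/40) = 0.0605.
- ln(0.50/0.40) = 0.223; 0.223/0.0605 − 1.96 = 1.73; power 95.8%.
- The other three BoExp have power of essentially 1, so the product is 95.8%, against 96% in Protocol Table 18.

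The sample size was therefore calculated for a test of the log-scale ratio against 0.50.

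**2. What another transformation does to the ratio.** Take a square-root analysis with illustrative CC levels. A halving from 6 to 3 is a difference of √3 − √6 = −0.717. Applied to other CC levels, the same difference gives:

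- CC 4: (2.000 − 0.717)²/4 = 0.41
- CC 6: (2.449 − 0.717)²/6 = 0.50
- CC 8: (2.828 − 0.717)²/8 = 0.56

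One fixed difference thus corresponds to different ratios and cannot by itself be read as a 50% reduction.

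**3. Error rates at a true ratio of exactly 0.50 (nominal 2.5%, one-sided).** Two set-ups were simulated. One is the planned ANCOVA with arms 80/40/40, adjusting for log baseline, sex and consumption (8,000 to 40,000 runs; Monte Carlo standard error 0.08 to 0.17 points). The other is a two-sample comparison, 80 vs 40, with COHb CV 0.32. The rank test is applied to log values shifted by ln 0.5.

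| Situation | Analysis | Error |
|---|---|---|
| Same shape and variance in all arms | Log-scale ANCOVA: normal / t with 3 df / right-skewed / left-skewed / strongly skewed | 2.4 / 2.3 / 2.8 / 2.1 / 3.0% |
| Same | Fixed rule: Shapiro-Wilk p<0.05, then rank test | 2.0–2.6% (ANCOVA set-up), 2.4–2.8% (two-sample) |
| Same | More favorable of ANCOVA and rank test | 3.0–4.6% |
| Same | Best of log, rank and square-root (two-sample) | 3.2–4.6% |
| THS 2.2 right-skewed, CC lognormal (two-sample) | Shapiro-triggered switch to rank test | 11% |
| Same | Log-scale test, pooled / separate variances | 3.7 / 3.1% |
| Shapes differ between arms | Rank test, judged against the geometric-mean-ratio null | 9–29% in unfavorable cases, 0.1–1% in the reverse direction |
| Shapes differ, equal variance | Log-scale ANCOVA | 1.5–4.5% |
| LLOQ/2 pile-up in THS 2.2 and SA only | Log-scale ANCOVA | 1.9% |

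Upper bounds for free choice are 2 × 2.5% = 5.0% with two methods and 3 × 2.5% = 7.5% with three.

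**4. Unequal variances.** Protocol Table 16 gives COHb a CV of 0.20 for THS 2.2/SA and 0.32 for THS 2.2/CC. The documents do not say which arms each CV pools, so these are assumed readings, all with normal errors:

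- THS 2.2 CV 0.20 and CC CV 0.32, two-sample: 4.3% with pooled variance, 2.6% with separate variances.
- Three-arm ANCOVA over the four BoExp, THS 2.2/CC CV taken as the CC arm's own: 4.7–6.4%.
- Same, THS 2.2/CC CV taken as an equal-weight pool of the two arms: 6.1–8.0%; as a 2:1 pool: 7.1–8.8%.
- Separate-variance test on the log scale in these three-arm settings: 2.4–2.6%.

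**5. Timing.** The documents do not date the distribution check. Testing the model's assumptions needs residuals, hence arm codes, and SAP Table 2 keeps the statisticians blinded until the later of SAP finalization and database lock. A check on data pooled over arms would not settle the matter. With an expected MHBMA ratio of 0.15 and CV 0.70, the arm means lie |ln 0.15|/0.631 = 1.90/0.631 = 3.0 log SDs apart, so pooled data could look non-lognormal even if every arm is lognormal.

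**The case against.** The strongest reply is that the plan does name its primary analysis. SAP 12.6.1.1 and 12.6.1.2 give the log-scale ANCOVA, its code and the ratio with CI. The fallback stands in a preamble for all BoExp, is limited to marked departures and an appropriate method, and changes must be reported in the CSR. That stands as context, but it does not close the gap, because nothing exempts the primary endpoints.

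Several stronger readings are tempting, and the reply is right to resist them.

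- *The switch inflates the error by itself.* It does not. A fixed rule with same-shape arms stays near 2.5%. The excess needs free choice, or a rank test applied to arms of different shape. The text permits a choice but does not say that the most favorable method will be taken.
- *A non-parametric method cannot give a ratio.* It can. A rank-based shift estimate on the log scale, or a bootstrap of the geometric mean ratio, keeps one. The documents simply require neither.
- *The log-scale ANCOVA holds its level, so no alternative is ever needed.* This is supported only for similar shape and variance across arms. In two unequal-variance cases the shifted rank test was nearer nominal (3.4% and 4.8%) than the pooled log test (4.3% and 6.4%).
- *The check is made after unblinding.* This is likely, given the reference to model assumptions, but it is an inference. A pre-lock data review is also planned.
- *The seed rule makes the result arbitrary.* Recording the seed in the output supports reproducibility, and with enough resamples the seed matters little.

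**Conclusion.** The point holds as a specification gap with a real, conditional consequence. For any primary BoExp, the confirmatory analysis may be replaced on an undefined trigger by an undefined method that need not estimate the quantity in the success criterion. The study might then be unable to decide success on its own criterion; the documents do not show that it would be.

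In size, the one-sided error is about 2.5% if a fixed rule is followed with same-shape arms, about 3 to 4.6% with free choice, and above 10% where a rank test replaces the log-scale analysis and the arms differ in skewness. The last figure is measured against the geometric-mean-ratio null and assumes that the skewness runs in the unfavorable direction; in the reverse direction the test becomes conservative.

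Non-lognormality alone does not call for a switch when shape and variance are similar across arms. Unequal variances are a separate weakness of the pooled model. Its size of about 4 to 9% rests on an assumed reading of Table 16, and the free fallback is no reliable cure for it. This should be corrected, but it does not by itself invalidate the design.

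**What to change.** State in Protocol 12.4.4 and SAP 12.6 that, for the four primary BoExp, the log-scale ANCOVA ratio THS 2.2:CC and its two-sided 95% CI decide success whatever the distribution check shows, with the upper limit compared with 0.50. Write the null hypothesis with that margin. Preferably allow arm-specific residual variances, for example through a group option by product in PROC MIXED.

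Make any other transformation, rank method or bootstrap of the same ratio a sensitivity analysis, named in advance with the quantity it estimates. Fixing the seed beforehand is optional.

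The cost is wording and one option in the SAS code, with no new data or subjects. The price is a possible small loss of efficiency in very heavy-tailed data, where a rank method might have done better. The separate-variance results of 2.4 to 2.6% are for normal errors, so that option addresses unequal variances and should not be presented as a remedy for skewness.
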